NCT02669407

1. Protocol Title:

Splanchnic Nerve Block for Therapy of Acute Heart Failure (Splanchnic HF)

2. Purpose of the Study:

Splanchnic vasoconstriction may contribute to decompensation of chronic heart failure via volume redistribution from the splanchnic vascular bed to the central compartment. This is a sympathetically mediated reflex and can be interrupted through a splanchnic nerve block. Therefore, we hypothesize that interruption of the efferent/afferent innervation of the splanchnic vasculature will decrease cardiac congestion and improve renal function in patients presenting with heart failure.

Objectives:

- 1. We will determine if splanchnic nerve blockade decreases cardiac preload as measured by invasive hemodynamics.
- 2. We will determine if splanchnic nerve blockade increases urine output.
- 3. We will determine whether splanchnic nerve blockade produces rapid improvement in creatinine clearance.

3. Background & Significance:

[figure not shown]
Conventional wisdom dictates that heart failure (HF) exacerbations follow a period of fluid accumulation leading to volume overload. However, study of weight in HF shows that 54% of patients have an exacerbation without antecedent weight gain. Invasive monitoring of hemodynamics showed that central venous pressure rises in the weeks prior to decompensation despite no weight change in both systolic and diastolic heart failure. The leading theory for explaining this phenomenon of increased central venous pressure in the absence of change in total body water is that patients with heart failure (HF) have impaired ability to store blood in their splanchnic vascular compartment. In a healthy population, the splanchnic bed contains about 40% of the total blood volume, 80% of which is stored in capacitance veins, and serves as a buffer for the central vascular compartment. Fluid is normally mobilized from this compartment via increased sympathetic tone and circulating catecholamines in response to a variety of physiologic and pathologic stressors. Given the role that the splanchnic circulation plays in hemodynamic regulation, it is hypothesized that increased sympathetic tone in the splanchnic vasculature contributes to both acute and chronic heart failure decompensation by mobilizing fluid to the central vasculature (Fallick C, Circulation Heart Failure 2011).

Animal models provide direct evidence of this pathophysiological effect. In healthy animals, splanchnic nerve stimulation shifts blood into the central compartment, increasing preload and cardiac output. In dogs with cardiac pacing induced systolic heart failure, splanchnic vascular capacitance was decreased (Ogilvie RI, circulation 1992). In these dogs, surgical transection of the splanchnic nerve, terminating sympathetic tone, results in decreased preload as

measured by systolic and diastolic filling pressures and increased compliance of the left ventricle (Figure A). In humans splanchnic nerve blocks are commonly used for pain control in patients with intractable visceral organ cancer pain. The nerve blocks are done temporarily using anesthetic agents or more commonly permanently using neurolytic agents. Interestingly, the most common "sideeffect" of this therapy includes transient orthostatic hypotension due an increase in splanchnic vascular storage capacity, which typically is prevented by aggressive pre-procedural hydration (Eisenberg E, Anesthesia and analgesia 1995).

А

В

[figure not shown]

Figure B: Pressure-volume recording in left ventricle in same animal. Blue curves are the baseline recordings and red indicate pressure-volume loops after nerve transection. Nerve transection caused flattening of the end-diastolic pressure-volume relationship indicating higher compliance. Unpublished pilot data.

In addition to the strong evidence supporting splanchnic nerve blockade as treatment of volume overload, it is possible it will also treat cardiorenal syndrome. The autonomic nervous system plays a critical role in the regulation of the kidney. Though this system is not fully understood, preclinical and clinical studies indicate the presence of a hepatorenal reflex that inhibits the renal function and causes fluid retention. This reflex has its origin in the portal vein and is stimulated by portal congestion. The splanchnic nerves represent the afferent and partially the efferent arm of the reflex arch. Inhibition of this reflex pathway in animals and a small human pilot study was shown to improve renal function and urine production.

4. Design & Procedures:

This study will be a prospective, uncontrolled clinical trial. The study will not be controlled as invasive monitoring of hemodynamics will be performed, allowing clear demonstration of a cause-effect relationship. Furthermore, the goal of the study is to demonstrate proof of concept.

This study aims to piggy-back on an elective right heart catheterization (+/- left heart catheterization) in patients admitted for acute decompensated heart failure The right (+/- left heart catheterization) will be part of the subject's standard of clinical care (SOC). Subjects will undergo catheterization of the heart to obtain central cardiac pressure and other cardiac hemodynamic parameters found to be necessary by the primary team. This will occur in the cardiac catheterization lab. Once the SOC catheterization procedure is completed the subject will undergo, as part of this clinical study (CS), a regional nerve block (bilateral splanchnic nerves) while they are in the catheterization lab. This will be performed by an anesthesiologist experienced in splanchnic nerve blocks. Routinely, patient will remain in the catheterization lab for the duration of anesthetic block and will be continuously hemodynamically monitored. Also, prior to elective catheterization procedure and following splanchnic block patients will undergo a number of vital, laboratory and imaging tests, which will be in parts SOC or part of the CS (see Table of Assessments below).

Table of Assessments

Table of Asses	Silicitits						
Required Assessment	<5 Days before procedure	Same day of procedure (<12h before procedure)	Procedure (1-1.5h)	Within 2 hours after Procedure	Day after procedure	48 h after procedure	6 Months after Procedure (±14 days)
Vitals (BP, HR, RR, SpO2)	X (SOC)	X (SOC)	X (SOC)	X (SOC)	X (SOC)	X (SOC)	
Weight	X (SOC)	X (SOC)		X (SOC)	X (SOC)	X (SOC)	
Orthostatic vitals	X (CS)			X (CS)	X (CS)		
Urine output (continuous recording)	X (SOC)	X (SOC+CS)	X (SOC)	X (CS) 3 and 8 hours post procedure	X (SOC+CS)	X (SOC+CS)	
Labs: BMP, pro-BNP, urine sodium,		X (SOC/CS)		X (CS) for pro-BNP and urine sodium	X (SOC) for BMP	X (BMP are SOC, no pro BNP needed)	
Labs (Angiotensin II), Plasma Metanephrines, Vasopressin, Plasma Catecholamines		X (CS)		X (CS)			
Dyspnea Questionnaire		X (CS)	X (CS)	X (CS)	X (CS)	X (CS)	
Six minute walk test	X (CS)	(03)	(03)	(CS)	X (CS)	(CS)	
Impedance and lung fluid content measurement			X (CS)	X (CS)			
Positional Change: Bending Over		X (CS)		X (CS)			
Positional Change: Leg Raise			X (CS)				
Heart rate variability	X (CS)	X (CS)	X (CS)	X (CS)	X (CS)	X (CS)	
Echocardiogram	X (SOC)			X (CS)			
Splanchnic nerve block			X (CS)				
Phone Call**	1 · · · · · · · · · · · · · · · · · · ·						X (CS)

*Plasma Metanephrines will be performed only if subject is on inotropes **Phone call will capture mortality status and number of subject admissions to the hospital since procedure

Following enrollment into the study the subject will undergo the following tests/measurements. A majority of the clinical testing occurs as part of routine clinical care and will be marked as SOC (like in the above table). Tests required only for the purpose of the study are marked with CS.

Pre-procedure: Following information will be collected from the patient charts that will

- be done as standard of care (SOC). Study specific tests/recordings are also listed below:
- If the subject is female and childbearing potential and has not had a pregnancy test since the arrival to the hospital, a blood pregnancy test will be done (CS). If positive the subject will be excluded from the study.
- Subjects will have strict measurement of urine output (SOC). Additionally, subjects will be asked to void 3 hours prior to their procedure. They will be asked to void again immediately prior to the start of the procedure. A urine sample will be sent to the laboratory to check for the sodium concentration (CS). Subjects requiring a foley catheter will have measurements taken at comparable time intervals (SOC).
- Recorded vitals including weight, BP, HR, RR, SPO2 on the day before procedure and within 1h before procedure (SOC) and record heart rate variability using a non-invasive wrist monitor for 5 minutes (CS).
- Orthostatic vitals (5 minutes supine, 1+5 minutes sitting and 1+5 minutes standing) on the day before procedure and within 1h before procedure (CS)
- Labs: Basic metabolic panel (BMP) (SOC), brain natriuretic peptide (BNP) (SOC/CS), plasma angiotensin II (CS), plasma arginine vasopressin (CS), plasma catecholamines. Plasma metanephrines (CS) will be performed if subject is on inotropes. This will not require an extra lab draw. Total expected blood loss is <20ml.
- Dyspnea questionnaire using a 7-point Likert scale and Visual Analog Scale (CS)
- Six minute walk test (CS)
- Echocardiogram during the admission and no longer than 5 days prior to study (SOC). If no up-to-date echocardiogram is present, a study related Echocardiogram will be obtained (CS).
- If the patient is on diuretics medications the scheduling of the medication will be adjusted to minimize interference with the study intervention.

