2. Bilateral splanchnic nerve block performed by an anesthesiologist (see images below) (CS). Following the right heart catheterization procedure the patient will be prone on the abdomen. Central venous access remains in place. Needle will be placed under fluoroscopic guidance in the posterior chest wall. Anesthetic solution (1% lidocaine with epinephrine) (1:200.000) will be injected (10-15 ml on each side). Patient will then be placed back on his/her back and central

hemodynamics are recorded again for the next 1-1.5 hours, approximately every 15 minutes. The central venous catheter will be removed after the hemodynamic monitoring is completed in the catheterization laboratory. Unless the primary team requested the catheter to remain in place and the patient is moved to the intensive care unit.

Following the block, the subject will repeat the positional change of a leg raise at 30, 60, and 90 minutes post-block to observe any changes in shortness of breath symptoms.

Additional measurements include:

- Orthostatic vitals will be obtained at the end of the hour while in the catheterization lab (CS).
- Dyspnea questionnaire (CS)
- If medically indicated a Swan Ganz catheter will be left in place. This would enable continuous monitoring of central hemodynamics for the next 24h (q4h) (SOC).

Follow up procedures:

Following right heart catheterization and lidocaine splanchnic nerve block the patient will be monitored on the floor/CCU for at least 48 hours following nerve block (SOC).

- Continuous recording of urine output for 24 hours (SOC). They will then be asked to void again 3 and 8 hours after the placement of the nerve block and 24 hours after nerve block (CS).
- Basic vitals (SOC) and orthostatic vitals (CS) within 24 hours after nerve block, and record heart rate variability using a non-invasive wrist monitor (CS).

- Repeat labs 12-24 hours after nerve block (next morning) [BUN (SOC), BMP (SOC) and pro-BNP (CS)
- Labs: Angiotensin 2, plasma metanephrines (if on inotropes), plasma catecholamines, vasopressin and urine sodium will be collected immediately before and after the procedure
- Dyspnea questionnaire at 12-24 hours after nerve block (CS) and again at 48 hours
- Six minute walk test (CS) within 24 hours after block and again at 48 hours
- Weight the next morning after nerve block (SOC) and at 48 hours.
- Echocardiogram within 1-2 hours after nerve block (CS)

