- Positional change of bending over to evaluate 'bendopnea' (shortness of breath symptoms with bending over).

Phone Call

Subjects will be contacted by study team six months (\pm 14 days) following their nerve block procedure. The purpose of this call will be to obtain mortality status and document the number of inpatient admissions since the procedure.

Blood samples processing:

Some blood samples collected before and after the nerve block (plasma metanephrines, plasma catecholamines, angiotensin II and arginine vasopressin) will be processed (centrifuged) and stored at -70 degrees Fahrenheit before sent out to an external lab. Storage duration may vary between weeks to months. Samples will be stored in a research freezer located on the 7th floor of Duke North (cath lab research freezer). As part of the study, we will send blood for study-related laboratory tests to the Mayo clinic and Inter Science Institute. These would include laboratory tests such as metanephrines, vasopressin, catecholamines, and angiotensin.

Safety endpoints:

- The duration of the anesthetic block is estimated for 1.5 hours. The subject will be monitored for up to 1.5 hours in the catheterization laboratory (acute safety). Chronic safety up to 48 hours post procedure. Hereby the patient will be observed clinically on the floor or CCU per standard clinical care routine. Further the subject's medical chart will be observed for 6 months following study enrollment to evaluate for recurrent admissions for heart failure.

Incidence of major side effects like:

- Pneumothorax, possibly requiring a chest tube
- Aortic puncture with retroperitoneal bleed or hematothorax
- Spinal cord trauma with possibly paralysis

Incidence of minor side effects like:

- Orthostatic hypotension
- Pain at puncture site and intercostal neuralgia

- Gastrointestinal dysmotility including diarrhea, constipation and abdominal cramping
- Bleeding at puncture site

Efficacy endpoints:

The following efficacy endpoints will be evaluated:

- Primary: Reduction in central venous pressure and/or pulmonary artery pressure (diastolic) and/or pulmonary capillary wedge pressure at 30-60 minutes after nerve block
- Secondary: Increase in cardiac output, improvement in echocardiographic parameters like ejection fraction (increase), central venous pressure (decrease), pulmonary artery systolic pressure (decrease), right ventricular diameter (decrease), left ventricular diameter (decrease)

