Descriptive statistics of continuous outcomes will include sample size, mean, median, standard deviation, minimum and maximum. For categorical outcomes, the number and percentage of subjects in each category will be presented. Statistical comparisons will be made using t-tests for continuous outcomes and chi square or Fisher's exact test (depending on overall event rates) for categorical outcomes. Paired t-tests will be used to compare changes from baseline to post-intervention. All statistical analyses will be performed using SAS for Windows (version 8.2 or higher) or other widely accepted statistical or graphical software. Patient data listings and tabular and graphical presentations of results will be provided. Unless otherwise specified, a two-sided 0.05 level of significance will be used to declare change in pre- and post-procedure variables different.

For power analysis, our primary endpoint is decreased in central venous pressure following nerve blockade. Based on preliminary animal experiments, we anticipate a reduction of CVP of 25%. For a sample size of 16, If the true difference in the experimental and control means is 25%, we will be able to reject the null hypothesis that the population means of the experimental and control groups are equal with probability (power) .90. The Type I error probability associated with this test of this null hypothesis is 0.05.

There is no direct measure of technical success following attempted block of the splanchnic nerves. The location of the splanchnic nerves is estimated biased on human anatomy dissections and established nerve block protocols used by the anesthesiology department. Procedural success to block the splanchnic nerves will be assumed in 70% of the cases based on the experience in splanchnic nerve blocks in patients with intractable cancer.

13. Data & Safety Monitoring:

Due to the experimental nature of this intervention, data will be recorded after each subject completes the intervention for signs of unintended negative effects. These include hypotension, worsening renal function, or clinical deterioration. Additionally, patient's electronic medical data will be clinically screened for any traumatic complications from the nerve block for the first 24 hours postprocedure.

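### The baseline echocardiogram may be up to 5 days old while the follow-up comes 1-2 hours after the block, so the secondary echo changes can mix inpatient treatment with the block effect

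*Combined protocol and SAP*

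**What the plan says.** **Baseline echo.** The pre-procedure list in Section 4 asks for "Echocardiogram during the admission and no longer than 5 days prior to study (SOC". The fallback is: "If no up-to-date echocardiogram is present, a study related Echocardiogram will be obtained (CS". The Table of Assessments agrees. Before the block, echo is marked only under "<5 Days before procedure", and the same-day column (less than 12 hours before the procedure) is empty for echo.

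**Follow-up echo.** Section 4, Follow up procedures: "Echocardiogram within 1-2 hours after nerve block (CS".

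**Endpoints.** The secondary efficacy endpoints in Section 4 include "improvement in echocardiographic parameters like ejection fraction (increase), central venous pressure (decrease), pulmonary artery systolic pressure (decrease", followed by decreases in right and left ventricular diameter.

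**Design and analysis.** Section 4: "This study will be a prospective, uncontrolled clinical trial". Section 12: "Paired t-tests will be used to compare changes from baseline to post-intervention", at a two-sided 0.05 level. Nothing in either section records, limits or adjusts for the time between the baseline echo and the block.

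**The concern.** Every subject is an inpatient under treatment for decompensated heart failure, some on inotropes (Section 5). A change measured from an echo several days old contains whatever that treatment did in the meantime, as well as anything the block did. With no control group, the paired test cannot separate the two.

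Section 4 defends the uncontrolled design on the ground that invasive monitoring shows cause and effect. That holds for catheter pressures read just before and after the block. It does not extend to an echo taken from the chart. Elsewhere the protocol does protect attribution: it re-times the procedure-day diuretic, and it puts the laboratory, dyspnea and bending-over baselines on the same day.

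At stake is whether a significant change in ejection fraction, echo CVP, PA systolic pressure or chamber diameter can be read as an effect of the block. Ordinary decongestion would be expected to move CVP, PA systolic pressure and the diameters in the direction the protocol counts as success.

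**Working it through.** **The plan's own figure.** No size or power is stated for the echo endpoints. The only power figure (Section 12) is 0.90 for a 25% fall in CVP at n = 16, with no SD. A two-sided paired t-test at 0.05 reaches 0.90 at n = 16 when the standardised change is 0.868, which implies an SD of 25 / 0.868 = 28.8 percentage points. The documents neither confirm nor refute that SD, and this point does not depend on it.

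**Timing.**
- Baseline echo to procedure: up to 5 days × 24 h = 120 h (Section 4 text and table).
- Block to follow-up echo: 1-2 h (Section 4, Follow up procedures).
- Estimated duration of the block: 1.5 h (Section 4, Safety endpoints).

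The text counts the 5 days back from the study and the table counts from the procedure. Section 7 sets enrollment at consent, so on one reading the gap could be slightly longer. I use 120 h.

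**What the plan controls in that interval.**
- Diuretic timing is adjusted on the procedure day only (Section 4).
- Newly started heart failure drugs exclude a subject only if begun in the preceding 48 hours. The drugs listed as examples include neither diuretics nor inotropes (Section 5).
- Other medications continue (Section 4).

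These are partial safeguards. Ongoing diuretics and inotropes before the procedure day, and new drugs started on days 3-5 before it, remain uncontrolled.

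**Effect on the test.** Let the true block effect be zero, and let δ be the mean drift between the two echoes in units of the SD of the paired difference. The paired t statistic is then noncentral t with n − 1 degrees of freedom and noncentrality δ√n. At n = 16, √n = 4, so δ = 0.2, 0.3 and 0.5 give noncentrality 0.8, 1.2 and 2.0. The documents give no echo SD or rate of change, so every δ is an assumption.

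Probability of a two-sided p < 0.05 with an inactive block:

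| Assumed drift δ | n = 10 (one EF group) | n = 16 (power statement) | n = 20 (maximum) |
|---|---|---|---|
| 0 | 5.0% | 5.0% | 5.0% |
| 0.1 | 5.9% | 6.6% | 7.1% |
| 0.2 | 8.8% | 11.6% | 13.6% |
| 0.3 | 13.6% | 20.3% | 24.7% |
| 0.5 | 29.3% | 46.5% | 56.5% |

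δ is a mean over all subjects analysed. If half had a recent baseline with no drift and half drifted by 0.4 SD, the mean would be 0.5 × 0 + 0.5 × 0.4 = 0.2 SD (ignoring the small extra variance). Five days is a maximum, and the documents do not give the distribution of intervals.

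**The case against.** The strongest reply is that the consequence is limited and the direction unproven.

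- **The primary endpoint is safe.** Its baseline pressures are recorded in the same session, just before the block, and readings follow about every 15 minutes. The power statement rests on CVP alone. Echo is one part of the secondary endpoints in a proof-of-concept study of up to 20 subjects. This stands in full.
- **Two echo measures can be checked.** CVP and PA pressure are also measured by catheter in the same session. This stands, although the plan does not ask for the comparison, and ejection fraction and the two diameters have no catheter counterpart.
- **Selection works against large improvement before the block.** Section 5 prefers diuretic-resistant subjects with low urine output in the 24 hours before enrollment. Sections 4 and 5 intend to drop patients whose filling pressures are not raised at catheterization. (Section 4 gives as its definition of decompensation the same wedge limits that Section 5 uses to exclude; the passages must be reconciled, but the intent is clear.) Some subjects may therefore be static or worsening. This stands in part: the urine-output criterion is only a preference, and a partly improved patient can still enter.

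A reader might go further and infer that the bias must favour the block, or multiply an assumed daily fall in PA systolic pressure (say 1-2 mmHg) by 5 days to reach a spurious 5-10 mmHg improvement. The documents do not support either step. They give no daily rate, selection makes the direction uncertain, and applying the maximum window to every subject overstates a mean.

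**Conclusion.** The point holds for the secondary echo endpoints only. As written, the paired test can attribute up to about 120 hours of inpatient treatment to a block of about 1.5 hours. The two safeguards in the plan reduce this but do not remove it.

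The bias may favour a positive result, but its direction and size cannot be fixed from the documents. With zero drift the error rate stays at 5%. With an assumed 0.2 to 0.5 SD it is about 12% to 47% at n = 16. That range shows how sensitive the test is; it is not an estimate of the actual bias.

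The finding does not undermine the primary hemodynamic result. It is a matter the sponsor should correct, at low cost, and not a reason to question the study as a whole.

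**What to change.** 1. Where the protocol already requires a study echo because no up-to-date one exists, mark it in the same-day (less than 12 hours) pre-procedure column of the Table of Assessments.
2. Record the date and time of every baseline echo and report the echo-to-block interval. State that the 5-day limit counts back from the procedure, so that text and table agree.
3. In Section 12, state that echo changes from baselines not taken on the procedure day are reported descriptively, as exploratory and not attributable to the block. Show echo CVP and PA pressure beside the same-session catheter values.

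**Cost.** Analysis wording, one recorded date and time per subject, and a scheduling rule for an echo already in the plan. No procedure is added and treatment is unchanged. The downside is fewer formal p-values for the secondary echo endpoints, perhaps none. Any subset with a procedure-day baseline will be small and selected, since it will consist largely of subjects with no up-to-date clinical echo.

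Testing only subjects with a baseline within 24 hours is a possible alternative, but the cut-off is arbitrary and could leave very few of at most 20 subjects. Descriptive reporting with the interval shown keeps every subject.
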